7.1. Study setting and population

The sampling frame for the pilot trial is geographical areas of high deprivation (IMD deciles 1-4) where diets are below average in FV consumption in the UK according to PHE Public Health Profile '5-a-day' indicator (https://fingertips.phe.org.uk/search/fruit). The intervention is targeted at streets (the unit of randomisation).

7.2. Area level consent

Over-arching consent for the areas to take part in the study is obtained from each local authority (via consultation with Public Health teams, community leaders and councillors). This method for consenting areas has been successfully used in area based public health voucher based intervention trials (Relton et al, 2018).

7.3. Eligibility criteria

Clusters (streets)

- High deprivation (IMD deciles 1-4)
- Below average (<2.7) number of daily portions of FV per person consumption for area

Participants (households)

- Private residential households

7.4. Intervention

The intervention (Fresh Street scheme) is described below using the Template for Intervention Description and Replication (TIDieR) checklist (Hoffmann et al, 2014). The pilot will enable us to deliver the intervention in different sites (objective a), assess uptake and identify factors which may impact on intervention success (objective b), create a manual describing a potential new public health intervention (Fresh Street) (objective c), (see Section 7.9 Data collection) and improve our ability to evaluate the intervention in the main trial (objectives d & f).

Item 1. Brief name : Provide the name or a phrase that describes the intervention	Fresh Street A place-based household voucher approach to increasing fruit and vegetable consumption.
Item 2. Why: Describe any rationale, theory, or goal of the elements essential to the intervention	The Fresh Street combination of fiscal measures with regular multi-faceted communication/ marketing information is designed to reduce food insecurity, increase daily consumption of fresh FV, and improve dietary quality, support healthy dietary habits, increase exposure to healthy food prompts. The goal is to help re-orientate local food systems so that they support healthy eating patterns, and advance the economic, social and environmental goals which impact on health in the longer term.
Item 3. What (materials): Describe any physical or informational materials used in the intervention, including those provided to participants or used in intervention delivery or in training of intervention providers.	Intervention materials delivered weekly in branded envelopes to individual households. Each envelope contains a letter to households with £5 worth of Fresh Street branded paper vouchers redeemable with local independent FV retailers (not supermarkets), a healthy and seasonal vegetable based recipe and nutrition and health/diet related information. Letters may include additional content e.g. encouraging households to share unused vouchers. A branded website offers online information. Branded posters displayed at participating FV retail outlets to show they accept Fresh Street vouchers.
Item 4. What (procedures): Describe each of the procedures, activities, and/or processes used in the intervention, including any enabling or support activities	Printing of secure, traceable, vouchers by A1 Security Print https://www.a1securityprint.com/ , redeemable at local FV retailers Training of FV retailers (what items vouchers can be used for and how to redeem the vouchers) Writing weekly covering letters Printing letters and packing envelopes and delivering envelopes

Table 1: Intervention description using the TIDieR checklist

	FV shopping and spending of vouchers by participants Redemption of vouchers by FV retailers, scanning unique QR codes using online app developed by A1 Security Print Reimbursement of voucher value
Item 5. Who provides : For each category of intervention provider (for example, psychologist, nursing	A1 Security Print have expertise in the production of secure cash transfer processes. Their clients include retail, education, government and banking.
assistant), describe their expertise, background and any specific training given	Local council staff bring their understanding of socio- economic conditions and public health issues in their local areas supplemented by the experience gained by QMUL staff in previous Fresh Street feasibility studies.
	FV retailers engage with households (customers) and are experts in the supply and use of FV in each local area.
	Community partners recruited to facilitate the weekly delivery of envelopes. This will involve local community and charity groups e.g. Good Gym (www.goodgym.org) a social enterprise which engages in community activities.
Item 6. How: Describe the	Envelopes delivered by hand by community partners or local
modes of delivery (such as face to face or by some other	staff.
mechanism, such as internet	FV picked up by participants or delivered to their door
or telephone) of the	
intervention	
Item 7. Where: Describe the	Fresh Street is designed to be delivered in areas of high
type(s) of location(s) where the intervention occurs,	deprivation (IMD deciles 1-4) and low fruit and vegetable consumption.
including any necessary	Fresh Street vouchers delivered by hand to households in
infrastructure or relevant	participating streets.
features	Fresh FV supplied by local market traders either in their own
	premises or through their existing delivery channels.
Item 8. When and how	Households receive the intervention (including vouchers
much: Describe the number of times the intervention was	worth £5) every week.
delivered and over	
what period of time	
Item 9. Tailoring: If the	The recipes and healthy eating messages adapted to
intervention was planned to	match the characteristics and resources in
be personalised, titrated or	each setting (e.g. dietary habits, ethnic profiles, food
adapted, then describe what,	geographies, and local priorities and resources) by the
why, when, and how	Fresh Street team in collaboration with local partners.
Item 10. Modifications: Item 11. How well	n/a
(planned): If intervention	We will explore the extent of any vouchers being used to purchase non FV items (i.e., 'trade' in vouchers) during
	paronase non r v items (i.e., trade in vouchers) during

adherence or fidelity was	qualitative interviews with local residents and by using
assessed, describe how and	'mystery shoppers' (Jumbe et al, 2019).
by whom, and if any	
strategies were used to	FV vouchers will be fully auditable in order to trace any
maintain or improve fidelity,	unusual or fraudulent activities.
describe them	

7.5. Sample size

Sample size for the pilot trial

The target for the pilot trial is 22 clusters (~300 households in each arm). - this is 33% of our main trial size and we think this is sufficient to enable us to address the objectives of the pilot.

There is no data from randomised trials that have used the portions of FV eaten yesterday questions on which to base a sample size calculation.

The original sample size calculation for the main trial (68 clusters with an estimated 856 households in each arm) was based on an increase of 0.5 in the number of portions of fruit and vegetables per person per day assuming a standard deviation of 2.0 (estimated for Health Survey for England 2017 taking into account our target population). This constitutes a small standardised effect size of 0.25. Stakeholder views of what constitutes a relevant increase in portions of FV eaten will be obtained during the pilot stage. Combining these with baseline cohort estimates of variability of portions of FV eaten will allow to assess whether effect size 0.25 will need to be revised and the required sample size be recalculated, changing the recruitment target for the main trial.

Sample size for process evaluation interviews

Semi-structured interviews (phone or face to face) will be conducted with up to 15 intervention households and up to 6 control householders or until data-saturation is reached. A purposive sampling strategy will then be adopted to ensure a full range of views, typical of the wider population. Maximum variation samples will be attempted based on (as far as possible): households who joined the Fresh Street scheme, households who dropped out of the scheme, and those with different ages, genders and ethnicities. All vendors will be contacted and invited to take part in interviews 3-4 months after the start of the intervention delivery.

7.6. Randomisation and allocation

In each site the council chooses an area which comprises a number of streets with between 500 - 1200 households per site (1200 = maximum size for a LSOA). A proportion of eligible streets in these sites will then be randomised to either the intervention or control. The allocation ratio will be 1:1.

Stratified (by site) permuted blocked randomisation with block sizes of m=6 and 4 will be used to ensure a similar number of clusters within each arm. The randomisation will be carried out remotely by the PCTU. One researcher per site will be un-blinded and will be authorised to request randomisations. An independent statistician from the PCTU will generate randomisation lists and will return the cluster allocations to the un-blinded researcher via

email. Further details will be explained in the Data Management Plan which will be agreed and signed off between the trial study team and PCTU.

7.7. Blinding

Due to the nature of the intervention pilot trial participants cannot be blinded to treatment allocation if they are in the intervention arm and neither can the researchers working on the field and/or at Council level. However, those involved in writing the statistical analysis plan and assessing the data will remain blinded to participant's allocation until the point of analysis.

7.8. Recruitment

The participating sites (listed below and in the study collaborators section) have already been recruited and their process of recruitment is not described here. Whilst more may be added in the future, the **sites** currently involved in the Fresh Street project are as follows: (1) Doncaster Metropolitan Borough Council, (2) Bradford Metropolitan Borough Council and (3) London Borough of Tower Hamlets Council.

All sites will be included in the pilot once they have the relevant approvals.

N.B. **Separate** HRA approval will be sought for members of the Grounded Research Team (based at RDaSH NHS Foundation Trust) to support the evaluation and deliver the intervention during the pilot.

Strategies for data collection to support the evaluation

There are substantial long-standing barriers to recruitment and public participation in health research (lack of saliency, lack of trust, and concerns relating to lack of privacy and agency), particularly from those groups characterised as 'hard to reach'. These barriers were experienced during the evaluation of the Fresh Street feasibility study in an area of high deprivation in Barnsley (Relton, 2020). Householders were invited to complete a health questionnaire (Yorkshire Health Study). Although there was high uptake of the intervention, >90% of householders declined to complete the health questionnaire. This was in part due to concerns that information might be shared with the Department of Work and Pensions (DWP).

In order to ensure that we obtain sufficient valid information to enable a robust evaluation of the intervention in this study we are adopting a range of strategies to build trust and increase saliency and thereby maximise survey response rates:

- Door knocking with face to face request/help to complete survey by local people with letterbox delivery of survey (with pen and SAE) for non-responders
- Minimising requests for more personal/ sensitive information
- Attractive easy to complete survey format
- Framing the surveys by highlighting the locality (e.g. Doncaster), the topic (Food, Health) or issue (COVID, climate change),
- Minimising survey length
- Offer of local supermarket voucher (or donation to local food bank)
- Primary research questions at survey start, personal questions at the end

Hand written address on the envelope

The pilot and process evaluation will enable us to assess the feasibility and utility of these strategies using survey responses and web traffic data and identify the most effective combination of approaches.

7.9. Data collection

During the pilot we will collect a wide range of quantitative and qualitative data to enable us to assess uptake of the intervention, and identify factors which may impact on intervention success (objective b).

The pilot will enable us to test, refine and optimise our household survey data collection methods (objective d) for the main trial and process evaluation (objective g). We aim to demonstrate that we can obtain baseline primary outcome measure responses from at least 50% of households (objective e).

The **primary outcome measure** for the pilot trial is portions of FV eaten yesterday. This information is asked using two questions from the Active Lives Survey questions (Sport England Active Lives Survey April 2020). This survey asks about healthy lifestyles and leisure, recreational, and cultural activities. It is conducted annually on behalf of government agencies including Sport England, Arts Council England and Public Health England by Ipsos MORI, an independent social research organisation. The survey is sent out to a randomly selected sample of households across England and completed online or on paper. The overall sample size is around 175,000 people for each survey with a minimum annual sample size for each English local authority of 500.

The two questions are:

"How many portions of fruit did you eat yesterday? Please include all fruit, including fresh, frozen, dried or tinned fruit, stewed fruit or fruit juices and smoothies. Fruit juice only counts as one portion no matter how much you drink."

"How many portions of vegetables did you eat yesterday? Please include fresh, frozen, raw or tinned vegetables, but do not include any potatoes you ate. Beans and pulses only count as one portion no matter how much of them you eat."

Extra information on what counts as a portion is provided alongside these two question (see Appendix 1 Full FV Tower Hamlets survey).

The **secondary outcome measures** include: Diet Quality (Roberts et al, 2018), food insecurity (Cafiero et al, 2018), long-term health conditions (Green et al, 2014), health-related quality of life (Rabin and Charro, 2001), and life satisfaction (Green et al, 2014). Secondary outcomes which are most likely to be impacted are listed in order.

The majority of the primary and secondary outcome measure data will be self-reported data from adults living in households in the streets.

The range of data that we plan to collect during the pilot is described in **Table 2. Data** collections tools and sources.

Surveys

Primary and secondary outcome data for the trial will be collected by contacting all households in the intervention and control clusters and asking one adult from each household to complete a survey. Collection of baseline data in the pilot will be completed before the introduction of the intervention.

If the decision is made not to progress to the main trial and/or the intervention ceases to be delivered then we will supplement baseline survey data with outcome survey data from households in all of the pilot clusters (objective j). We will use a repeated cross sectional trial design (i.e. the survey respondent from each household may not be the same at each data collection time point and respondents may also be from a different household if a new household moves into the house). This will enable us to obtain a representative picture for each of the streets.

The pilot will help us find ways to maximise survey responses (see section 7.8). We will find the best ways to frame questions (especially the primary outcome questions) by iteratively refining the script already developed. We will assess which questions need to be excluded from the survey either because householders perceive questions as irrelevant or sensitive e.g. ethnicity, vaccine status, or because the survey is too long.

Paper and/or online surveys

In the pilot we will begin with the paper survey. The research team will door knock every house in each of the streets and ask respondents to complete survey. If no one answers then the survey will be put through the letterbox with pen and stamp addressed envelope. After the first 200 households have had a chance to respond using the paper survey, if the response is insufficient (<50% provide baseline data) we will then introduce online surveys in addition to paper surveys. Using a cut-off of 200 responses will enable us to compare response rates and participant characteristics from paper and paper plus on-line surveys at the end of the pilot. After 200 responses the maximum margin of error around our assessment of response rate will be 7%.

If we collect data using both paper and on-line methods, then we need to decide whether one method gives a better representative sample than the other or whether to use both methods (and if so in what order/ time sequence).

We aim to ensure that we obtain valid unbiased data (RoB 2 for cluster randomized trials) (see section 7.10). Surveys will only be valid if both the name of the street and the house number is provided. This will be the case for both paper and on-line surveys. If we receive two or more valid responses (paper or paper and online) from the same household, then we will consider the paper survey response as the primary response. If two or more valid online surveys are received then we will consider the first valid online response as primary if there is no paper response.

Questions in the paper and the online surveys will be exactly the same. Paper surveys will be branded for each site e.g. Tower Hamlets Food and Health Survey (see Appendix 1).

However, the online surveys come in three different formats and have the following names: "What do you eat?", "Do you have enough to eat?" and "Virus Health and Wellbeing checKer (V-HAWK)". (see Table 2)

These online surveys will be integrated into QMUL 'Healthy People, Healthy Places' online platform (https://qmul.citizenlab.co/en/).

		Online
Data item	Measure/ Source	survey
		name
Primary outcome data		
Portions of FV eaten yesterday	Active Lives Survey	What do you
	(two questions)	eat?
Secondary outcome data		
Diet Quality Score (in the past month)	Diet Quality	What do you
	Questionnaire (DQQ)	eat?
Food insecurity (in the previous 12 months)	Food Insecurity	Do you have
	Experience Scale	enough to
	(FIES)	eat?
Long term conditions (fatigue, pain,	Questions from the	Virus-Health
insomnia, anxiety, depression, diabetes,	Yorkshire Health Study	And
breathing problems, high blood pressure,	(YHS) Health	Wellbeing
heart disease, osteoarthritis, stroke, cancer,	Questionnaire	checKer (V-
long COVID, other)		HAWK)
Virus symptoms, COVID diagnosis		V-HAWK
Life satisfaction	YHS Health	V-HAWK
	Questionnaire	
Health Related Quality of Life	EQ-5D	V-HAWK
Healthcare utilisation (last 3 months)	YHS Health	V-HAWK
	Questionnaire	
Free text comments (diet and health)		What do you
		eat
		V-HAWK
Respondent and hous	sehold information	

Respondent Ethnicity, Age group, Gender, COVID vaccine status, Consent to contact. Household Composition Street name and house number

For qualitative interviews conducted with householders, brief topic guides will be developed and piloted, and interviews either recorded by the field researcher using written notes or digitally recorded and transcribed depending on the preferences of the interviewee.

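### The 7% margin for the survey-mode switch is stated for 200 responses but calculated for 200 independent households, and the mode comparison that follows is sequential

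*Protocol*

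**What the plan says.** Protocol Section 7.9, under paper and online surveys, starts with paper. The decision point is a number of households approached: "After the first 200 households have had a chance to respond using the paper survey", and then "if the response is insufficient (<50% provide baseline data) we will then introduce online surveys in addition to paper surveys".

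The next sentence treats the same cut-off as a number of completed surveys: "Using a cut-off of 200 responses will enable us to compare response rates and participant characteristics from paper and paper plus on-line surveys". The precision statement follows on that basis: "After 200 responses the maximum margin of error around our assessment of response rate will be 7" per cent. No confidence level, ICC or design effect is given.

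Section 7.9 also says that the survey script will be refined as the pilot goes on, and that the team will decide afterwards whether one mode, or both in some order, should be used. Section 7.8 says of site entry: "All sites will be included in the pilot once they have the relevant approvals". Section 7.5 gives 22 clusters and about 300 households per arm. Section 7.1 makes the street the unit of randomisation.

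**The concern.** A response rate is responders divided by households approached, so its precision depends on the number approached. A cut-off worded once as households and once as responses gives field staff two different stopping points, and the stated margin can belong to only one of them.

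The households also come in streets. Neighbours are likely to resemble each other in whether they respond, and the same surveyor or the same day may affect a whole street. A margin that treats the 200 as independent is then too narrow.

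The switch also creates the comparison that the protocol wants to use for choosing the main trial's survey mode (objectives d and g). Paper-only comes first. Paper plus online comes later, only if the first batch was low, and while the script is changing. A difference between the phases need not be due to mode.

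**Working it through.** **Inputs.** Cut-off 200, threshold 50% and stated margin 7% (Section 7.9). 22 streets and about 600 households (Section 7.5), so 600/22 = 27.3 households per street. Not given and therefore assumed: a 95% two-sided level, and an ICC for survey response by street of 0.01 to 0.10.

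**1. Reproduce the 7%.** At p = 0.5 and n = 200 households approached: 1.96 × √(0.25/200) = 6.93%. The stated figure is this value, with a design effect of 1.

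**2. Read the cut-off as 200 responses.**
- At 50% response: 200/0.50 = 400 households; margin 1.96 × √(0.25/400) = 4.9%.
- At 25% response: 200/0.25 = 800 households, more than the pilot has.
- The lowest rate at which 600 households can give 200 responses is 200/600 = 33%.
- If the trigger is met (below 50%), 200 households have given fewer than 100 responses. The two cut-offs are then different points in the survey.

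**3. Allow for streets.** Design effect DE = 1 + (m − 1) × ICC; margin = 6.93% × √DE. Two layouts are possible, because the protocol does not fix the order of door-knocking:
- whole streets in turn: m = 27.3, so 200 households are 200/27.3 = about 7.3 streets;
- spread over all 22 streets: m = 200/22 = 9.1.

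| Assumed ICC | DE, whole streets | Margin, whole streets | DE, spread | Margin, spread |
|---|---|---|---|---|
| 0.01 | 1.26 | 7.8% | 1.08 | 7.2% |
| 0.02 | 1.53 | 8.6% | 1.16 | 7.5% |
| 0.05 | 2.31 | 10.5% | 1.40 | 8.2% |
| 0.10 | 3.63 | 13.2% | 1.81 | 9.3% |

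A t quantile for about 7 streets widens the whole-street margins to 9.6%, 10.6%, 13.0% and 16.3%.

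**4. Precision of the mode comparison.** With about 200 paper-only and 400 later households, the half-width for the difference is 1.96 × √(DE × (0.25/200 + 0.25/400)). This is 8.5 points with independent households, and 10.5, 12.9 and 16.2 points at ICC 0.02, 0.05 and 0.10, before any bias.

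**5. Regression to the mean.** Suppose that the true response is the same in both phases and that online adds nothing. The first batch is followed by online only if it falls below 50%. At a true rate of 50% and ICC 0.05 (whole streets), the standard error is 10.5/1.96 = 5.4 points. The mean of a normal variable cut off above at its own mean lies 0.798 SE lower, so the first batch averages 0.798 × 5.4 = 4.3 points below the truth (2.8 points with no clustering). By the same method the shortfall is about 1.7 points at a true rate of 45% and 0.4 at 40%.

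**The case against.** The strongest reply is that 7% is correctly calculated for 200 households and so shows which denominator was meant: one word needs changing. That is right about the intention, but the text as written still gives two cut-offs.

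A second reply is that the ICCs are assumed and that nothing says streets are finished one at a time. This stands, which is why both layouts are shown. If the 200 are spread over all streets, the understatement is small. Any positive ICC still takes the margin above 6.93%.

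A third reply is that, for judging this pilot's own 600 or so households, a finite population correction applies (√(400/599) = 0.817). It reduces the independent margin to 5.7% and the whole-street margins to about 7.0%, 8.6% and 10.8% at ICC 0.02, 0.05 and 0.10. That is fair for forecasting the pilot's own rate. It does not help when the result is carried to the main trial's streets, which is the purpose of objectives d and g.

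Several stronger readings are tempting but not supported:
- **That the comparison is bound to favour paper plus online.** The gain of about 4 points needs a true rate near 50%. Section 7.8 reports that over 90% declined the questionnaire in the feasibility study, so much lower rates are plausible, and there the effect nearly vanishes. Above 50% it is larger, but the trigger seldom fires (about 17% of the time at 55%). Bias from time or script changes has no known direction.
- **That the first 200 will come from one site or be unbalanced by arm.** Three sites and 600 households average 200 per site, and entry depends on approvals, so this could happen. The protocol fixes neither the order of sites nor the arms of the first streets. Section 7.11 plans matched collection across arms, though its wording covers outcome data.
- **That the switch is a coin toss.** Any threshold rule is uncertain when the truth lies close to the threshold.

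Lastly, a false trigger only adds a response route, and the protocol claims no formal test of mode. Both points stand and limit the seriousness.

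**Conclusion.** The concern holds as a minor one. The cut-off and its margin are worded for responses, while the trigger and the arithmetic are for households approached. The 7% is correct only for 200 independent households at the 95% level. With an assumed ICC of 0.01 to 0.10 the margin is about 7% to 9% if the households are spread over all streets, and about 8% to 13% if whole streets are surveyed in turn. It should not be called a maximum.

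The comparison of paper with paper plus online is confounded by design with calendar time and script refinement, and possibly with site, depending on the order in which sites open. Regression to the mean can flatter the later phase if true response is near 50%. The comparison cannot by itself show which mode is better.

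A reader might infer that the go, amber or red decision is compromised. It is not: Section 6.3 counts households across the study streets, not the first 200.

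**What to change.** In Section 7.9:

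1. Use households approached as the single denominator for the trigger, the cut-off and the margin.
2. Restate the margin allowing for clustering by street, with the assumed ICC range shown, or label the 7% as assuming independent households.
3. Draw the first 200 households from streets in both arms and, where more than one site is open, from more than one site.
4. Describe the mode comparison as descriptive, with intervals that allow for street clustering, and say that it does not by itself establish which mode is better.

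Randomising the remaining streets to mode would remove the confounding with time, but it should not be required. About 400 households in about 15 streets would give some 200 per mode, and a half-width of 1.96 × √(DE × 2 × 0.25/200), about 12, 15 and 19 points at ICC 0.02, 0.05 and 0.10. That is wider than the sequential comparison and much wider than the 4-point bias that it would remove.

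The cost is a few sentences of protocol text and some planning of which streets are visited first. The stated margin will look less favourable, and the mode comparison will support a weaker conclusion.

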Factors known or thought to affect fruit and vegetable consumption are mainly related to socio economic status (SEC). Data on proxy markers for SEC will be collected in the pilot study (ethnicity, health related quality of life, long term conditions and multi-morbidity). Factors that might affect the uptake of the intervention will be assessed in the pilot (e.g. Household composition). Table 4 below describes the data collected to help the pilot evaluation and includes the rationale for collecting each type of data.

Rationale for data sought	Type of data included
Primary outcome measure	Portions of FV eaten yesterday (two Active Lives
	Survey questions)
Secondary outcome measures	Diet Quality Questionnaire (DQQ), Food insecurity,
	Long Term Health conditions, Virus symptoms,
	COVID diagnosis, life satisfaction, EQ-5D
To ensure unique response from each	House number, Street name
included household and to enable outcome	
analyses to adjust correctly for clustering	
To enable subgroup analyses (especially	Household composition (numbers in household,
comparison with DH funded Healthy Start	under 5 yrs, 5-18 yrs, 65yrs+)
Scheme)	

Table 4: Survey evaluation data

To understand characteristics of survey responders and help assess whether intervention and control group responders are similar/balanced	Ethnicity, EQ-5D, Long Term Health conditions, multi-morbidity, Household type; age and gender
Other types of data collected	
General information	Free text "any comments about your diet" question
Process data (paper)	Date survey distributed/ returned
	Whether accept voucher or not
	Doorstep conversation data
Process data (online)	Date survey distributed/ returned
	IP address

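### The duplicate-response rule ignores which online survey was completed and whether the fruit and vegetable questions were answered, so a household's primary response can lack the primary outcome

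*Protocol*

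**What the plan says.** All of the following is in Protocol Section 7.9 unless another place is given.

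- **Validity.** "Surveys will only be valid if both the name of the street and the house number is provided". This covers paper and online forms.
- **Paper against online.** Where one household sends two or more valid responses, "we will consider the paper survey response as the primary response".
- **Online only.** "If two or more valid online surveys are received then we will consider the first valid online response as primary", if no paper form was returned.
- **Content.** "Questions in the paper and the online surveys will be exactly the same". Section 7.13 also describes the online questions as identical. Yet the text in Section 7.9 continues: "However, the online surveys come in three different formats and have the following names", and it lists *What do you eat?*, *Do you have enough to eat?* and *V-HAWK*.
- **Table 2.** Each outcome measure has one online survey name. "Portions of FV eaten yesterday" and diet quality are under *What do you eat?*. Food insecurity is under *Do you have enough to eat?*. Long-term conditions, life satisfaction, EQ-5D and healthcare use are under *V-HAWK*.
- **Purpose of the address.** Table 4 (Section 7.11) gives the reason for collecting house number and street as "To ensure unique response from each" included household, and to allow for clustering.
- **When online opens.** Only if fewer than 50% have given baseline data once the first 200 households have been approached on paper.

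**The concern.** The precedence rule treats any two online surveys from one address as competing versions of the same thing. Table 2 says they may be different questionnaires, only one of which carries the primary outcome. A rule that picks by time of arrival, or by paper over online, can therefore pick a response that cannot contain, or does not contain, the FV answers while another response from the same address does.

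The count of households with FV data is the pilot's main quantitative result. Objective e (Section 5) asks for baseline primary outcome responses from at least half of households, Section 7.14 analyses that proportion, and the green, amber and red criteria in Section 6.3 turn on 50% and 25%. A rule that sets aside FV answers already given would push this proportion down.

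**Working it through.** The protocol gives no figure for the effect of this rule, so there is nothing to reproduce. The check is first one of reading, then a small enumeration.

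**1. Can the statements on content and the rule all stand?**

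| Reading | Sentence on identical questions | Table 2 survey column | Rule |
|---|---|---|---|
| Each online format carries every question | true | serves no purpose | works if the FV items are answered |
| The three formats together make up the paper form | true only of the set | true | can select a response without FV items |
| The rule is meant only for repeats of the same named survey | true only of the set | true | works online, but this limit is not written |

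No reading leaves all three intact as written. The second and third fit Table 2, and the text decides between them nowhere.

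**2. Following the rule literally.**

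- No paper form; *V-HAWK* completed first, *What do you eat?* second. The primary response is *V-HAWK*, with no FV data.
- Paper form returned with address but both FV items blank; *What do you eat?* completed online. The primary response is the paper form, again with no FV data.

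**3. How often, if completion order were random?** This is an assumption and is not in the protocol.

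- All three surveys completed: 3! = 6 orders, and *What do you eat?* is first in 2. Share with a primary response lacking FV = 4/6 = 2/3.
- Two surveys completed, one of them *What do you eat?*: 4 orders, and it is first in 2. Share = 2/4 = 1/2.

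**4. What that could mean for the response proportion.** Input from Section 7.5: about 300 households per arm, so 600. Assumed, with no basis in the protocol: 5% to 20% of households respond online only, and 25% to 100% of these complete *What do you eat?* plus at least one other survey.

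Households affected = 600 × online-only share × multi-survey share × (1/2 or 2/3).

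- Low: 600 × 0.05 × 0.25 × 1/2 = 3.75, or 3.75/600 = 0.6 percentage points.
- Middle: 600 × 0.10 × 0.50 = 30; times 1/2 = 15 (2.5 points), times 2/3 = 20 (3.3 points).
- High: 600 × 0.20 × 1.00 × 2/3 = 80, or 13.3 points.

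The effect is zero if online surveys never open, or if *What do you eat?* always comes first and no paper form with blank FV items outranks an online answer. With the rule applied within each named survey, the number affected in these online multi-survey cases is also zero.

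**The case against.** The other side has a good deal to say, and much of it stands.

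- **Nothing is said to be thrown away.** A reader might infer that later surveys are deleted. The text only names one response as primary, and does not forbid combining surveys by address. The answers would still exist. What is missing is any statement that they are to be combined, while Table 4 points to one response per household.
- **Validity on address alone.** A reader might infer that an address is enough to make a survey valid. The sentence is worded as a necessary condition, so it does not say this. It also does not add the FV answers as a condition.
- ***V-HAWK*-only households.** A reader might infer that these count towards progression. Sections 5 (objective e), 7.9 and 7.14 all speak of primary outcome responses, and such a household supplies none. Only the footnote in Section 6.3 is looser, asking for information from one person.
- **Selection by title.** It is tempting to say that a survey named *Do you have enough to eat?* draws those short of food. The documents contain no evidence for that. Framing surveys by topic is a deliberate strategy (Section 7.8) that the pilot is meant to assess.
- **Random order.** Section 7.8 puts primary questions at the start of the survey, and Section 7.9 names *What do you eat?* first. If that order were imposed online, the fractions would fall. The protocol does not say that it will be.
- **Conditional trigger.** Online surveys may never open, and the first-online rule matters only where no paper form came back. Against this, Section 7.8 reports that more than 90% declined the health questionnaire in the Barnsley feasibility study. Section 8.1 also allows a prize-draw entry for each valid online survey if online response is poor. Several surveys from one address are therefore foreseeable.
- **Left to other documents.** Handling of blank items is often settled in an analysis or data management plan. Here, however, the protocol itself fixes an order of precedence that takes no account of blank items.

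**Conclusion.** The point holds in a limited form. As written, the precedence rule can give a household a primary response without the primary outcome although FV answers were supplied from the same address. The statement that paper and online questions are the same also does not fit Table 2. The likely direction is an understated response proportion for objective e and the Section 6.3 criteria.

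The size cannot be derived from the protocol. The 1/2 and 2/3 fractions rest on random completion order, and the span of 0.6 to 13.3 points rests on assumed online uptake as well. They show only that the effect could range from negligible to relevant near a threshold. The documents do not support a claim that two thirds of online FV data will be lost. Because the answers could still be linked by address and the trigger is conditional, this should be fixed before online collection opens, but it does not undermine the pilot design.

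**What to change.** 1. State that the duplicate rule applies within each named online survey, and that different surveys from the same address are combined.
2. Define a valid primary outcome response as street name, house number and both FV answers. Use this definition in Section 7.9 and in the footnote to Section 6.3.
3. For the primary outcome, apply the existing order (paper first, then first online) only among responses with both FV answers.
4. Reconcile the statement that the questions are the same (Sections 7.9 and 7.13) with Table 2, by saying whether each online format carries all questions or the three together make up the paper form.

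The cost is a few lines of protocol text and matching data-handling instructions. Street name and house number are already collected on every form, so no new data are needed. One limit should be acknowledged: surveys combined by address may come from different adults. The age group and gender items listed in Table 2 would help to flag this, if they are asked in each online survey.
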